8.3.3 Analyses of Key Secondary and Other Secondary Endpoints

The same MMRM method applied to the primary efficacy endpoint will be used to evaluate the between-treatment difference for the key secondary endpoints and the other secondary endpoints using the FAS. The same treatment policy strategy as that applied to the primary efficacy endpoint will be used for the secondary efficacy endpoints analysis. Differences between the two treatment groups, the p-values, and the 2-sided 95% CIs will be calculated within the framework of MMRM. The model will include all terms as in the primary endpoint model except that the baseline values will be corresponding to the baseline value for each parameter. Note that only the post-baseline visits on which the endpoints are scheduled to be measured will be included in the model.

The main analysis population is the FAS. Similar sensitivity analyses as for primary endpoint will be repeated for the key secondary and other secondary endpoints. As supportive analysis, the key and other secondary endpoints will also be analyzed using the PPP, and CP. Additional sensitivity analyses using MMRM with Last Observation Carried Forward (LOCF) may be performed.

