# **Duration of Treatment**

Treatment duration with study drug will be 78 weeks. Subjects will participate in the study for up to 95 weeks: up to approximately 13 weeks for Screening, 78 weeks of treatment, and 4 weeks until the Safety Follow-up Visit.

Confidential Page 18 of 115

Subjects who discontinue the study drug during the trial will be encouraged to remain in the study (off study drug) for continued follow-up by attending Week 52 and Week 78 visits with select study-related procedures performed [retrieved dropouts (RDO)]. For those subjects who choose to completely withdraw from the study at any point, they will be encouraged to return at Week 78 to finish the aforementioned procedures.

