#### 7.2.14. Early Termination Visit

Early Termination is also considered an EOT visit. An ET Visit should be completed if a study subject discontinues prematurely from the study, or is discontinued from the study by the Investigator [see Section 5.5].

If a study subject prematurely discontinues from study treatment, an ET Visit should be conducted at the time of discontinuation. Every effort should be made to conduct all ET procedures as specified below and in the Schedule of Assessments [Appendix 2]. Every attempt should be made to follow study subjects who have an SAE for 4 weeks after their ET Visit. For subjects who continue to be followed for safety, SAEs should continue to be reported as described in [Section 8.4.2].

The following procedures will be performed. The recommended order is shown below:

- Vital signs (prior to blood draw)
- Physical examination
- Neurological examination
- Weight
- AE assessment
- Change in medications since last visit
- ADAS-Cog
- MMSE
- A-IADL
- CDR
- DAD
- NPI
- QoL-AD
- RUD Lite
- C-SSRS
- Single 12-lead ECG (triplicate if QTc prolongation observed previously or in current visit)
- Safety laboratory tests
- Plasma sample collection for biomarker assessment (exact time of sampling will be recorded)
- Plasma sample collection for PK assessment (exact time will be recorded)
- Urine for urinalysis
- Urine pregnancy test (female subjects of childbearing potential)
- Study drug dosing from the last dose prior to the visit (time of dosing will be recorded)

Confidential Page 78 of 115

- Study drug return, accountability, and compliance
- BP and pulse approximately 15 minutes after last blood draw
- MRI (as soon as possible, no later than 2 weeks after the ET visit)

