#### 7.2.15. Retrieved Dropout Visit

In addition to the ET visit, subjects who discontinue the study drug during the trial will be encouraged to remain in the study (off study drug) for continued RDO visits by attending Week 52 (if applicable) and Week 78 (EOT) visits. The RDO visits will include the following procedures, in the recommended order shown below:

- Vital signs
- AE assessment
- Change in medications since last visit
- ADAS-Cog
- A-IADL
- MMSE
- NPI

For subjects who prematurely withdraw from the study,, they will be encouraged to return at Week 78 to finish study-related procedures.

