ADAS-Cog 13 scores are assessed at Day 1 (Baseline), and Weeks 13, 26, 52 and 78. Observed ADAS-Cog 13 scores including those from unscheduled visits and early discontinuation, are assigned analysis visits based on the visit window using the assessment's study days. After applying a visit window, there is only one non-missing or missing value for each analysis visit. These data are called observed data and the change from baseline in ADAS-Cog 13 scores (observed data) for efficacy analyses are derived by subtracting corresponding baseline value at each visit. Other efficacy endpoints derivation follows the same algorithm.

Unless otherwise specified, all primary efficacy analyses will be performed using the FAS population. Analyses of the primary endpoint of ADAS-Cog 13 will be performed with a likelihood based MMRM on treatment observed cases (OCs). The observed data set will consist of actual observations recorded at each visit and missing data is not explicitly imputed. The model terms will include treatment, the stratification factors of use of concomitant AD medications (AChEI or none), age group (50-65 years inclusive or > 65 years through 80 years), gender, disease severity based on baseline MMSE (≤ 26 vs. > 26), baseline ADAS-Cog 13 values, visit (VISIT), and treatment-by-visit interaction. The visit variable will be used to define the within-subject covariance for the repeated measures over time. The least squares mean (LSM) for each treatment at each visit will be generated together with its 95% confidence interval, and the LSM difference between ALZ-801 and placebo will also be calculated; together with its standard error, and the 2-sided 95% confidence interval. The MMRM has an inherent mechanism to "implicitly impute" missing values when calculating the LSM of treatment effects which assume missing at random (MAR). For the primary endpoint at 78 weeks, treatment comparisons will be done at the 0.05 significance level.

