All data collected during the study will be used in the statistical analysis. Under the treatment policy strategy, measurements after occurrence of intercurrent events (subject withdrawal or dropouts for various reasons or use of symptomatic AD medications) will not be considered missing data and will be included in the primary analyses. For subjects who discontinue treatment prior to trial completion, every attempt will be made to have them continue with clinic visits and study assessments. Particular attention will be given to collecting Week 78 ADAS-Cog 13 assessments, regardless of when subjects discontinued treatment.

Note that only the post-baseline visits on which the endpoints are scheduled to be measured will be included in the model.

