8.3.2 Supportive and Sensitivity Analyses of the Primary Efficacy Endpoint

Supportive Analyses

As supportive analysis, the primary endpoint will be analyzed using the MMRM model on the per-protocol population and on completers. Additional supportive analyses may include MMRM with Last Observation Carried Forward (LOCF).

Additional supportive analyses will include the repetition of the primary analysis using the 'while-on-treatment' strategy on the FAS population. This strategy estimates the treatment effect before the occurrence of intercurrent events. These events include treatment discontinuation and the use of symptomatic AD medications (AChE inhibitors or memantine). Any data collected after the occurrence of intercurrent events will be considered as missing.

Sensitiviy Analyses

Multiple Imputations (Missing at Random, MAR)

As a sensitivity analysis, a similar MMRM model as the one applied to the primary endpoint analysis will be repeated using multiple imputation methods under the assumption of MAR.

Before conducting the multiple imputation, the missing data pattern will be examined. A dataset is said to have monotone missing pattern if the missing values always occur at the end of the longitudinal data, e.g., missing data after withdrawal.

A dataset is said to have non-monotone missing pattern if some subjects have missing values for intermediate visits but have available data at subsequent visits. If the ADAS-Cog data are deemed having monotone missing pattern, the standard multiple imputation approach using SAS PROC MI with regression method will be applied. If ADAS-Cog data are determined to have non-monotone missing pattern, the Markov Chain Monte Carlo (MCMC) method will first be applied to impute the intermittent missing data, and then the regression method will follow to impute the monotone missing data. In the case that the regression method cannot fully impute the missing data, the MCMC method will be applied to impute both monotone and non-monotone missing patterns. The example SAS programming codes using regression method for monotone missing pattern are:

```
PROC MI DATA=DATAIN OUT=DATAOUT NIMPUTE=100 SEED=999[to be changed]; CLASS TREATMENT ACHEI AGEGRP GENDER DISSTAGE; VAR TREATMENT ACHEI AGEGRP GENDER DISSTAGE BASE ...; [insert scheduled visits for ADAS-Cog 13 up to Week 78, i.e, V5 V7 ...] MONOTONE REGRESSION; RUN;
```

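### CDR-SB (H3) is declared under treatment policy, but no CDR is scheduled after the early-termination visit, so for subjects who stop study drug its MAR-based estimate approximates a treatment-continued effect

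*SAP*

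**What the plan says.** **Strategy.** SAP 8.3.1 (Table 16) names treatment discontinuation and use of symptomatic AD medication as intercurrent events and adopts treatment policy for ADAS-Cog 13. Measurements after such events "will not be considered missing data and will be included in the primary analyses". SAP 8.3.3 extends this to CDR-SB in one sentence: "The same treatment policy strategy as that applied to the primary efficacy endpoint will be used for the secondary efficacy endpoints analysis". Under SAP 8.1.5, H3 is tested at 0.025 once the primary succeeds, and at 0.05 if A-IADL (H2) is also significant.

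**Data.** Protocol 7.2.14: "If a study subject prematurely discontinues from study treatment, an ET Visit should be conducted at the time of discontinuation". CDR is on that visit's list. For those then followed off drug, Protocol 7.2.15 says "The RDO visits will include the following procedures, in the recommended order shown below", and CDR is not among them. The synopsis describes this follow-up as "by attending Week 52 and Week 78 visits with select study-related procedures performed".

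**Missing values.** SAP 8.3.1 states that the MMRM relies on MAR. In SAP 8.3.2 the sensitivity model "will be repeated using multiple imputation methods under the assumption of MAR". Methods that do not assume MAR are optional there and would be chosen after the unblinded data have been examined.

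**The concern.** Treatment policy asks what happens to everyone assigned to a treatment, including after they stop it. That needs outcomes collected after stopping, or an assumption about them. For CDR-SB none is scheduled, and MAR fills the gap mainly from same-arm subjects with similar histories who stayed on drug. If benefit fades off drug, the filled-in values are too favourable to the active arm.

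The stake is the meaning of a multiplicity-controlled result. H3 could be reported as a treatment-policy effect although, for discontinuers, its scheduled data cannot show one. If the while-on-treatment analysis is repeated for CDR-SB, it will use nearly the same data for this event. Its agreement with the main analysis would then be close to automatic and could be mistaken for robustness.

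**Working it through.** **1. Visit lists side by side** (Protocol 7.2.10, 7.2.12, 7.2.14, 7.2.15)

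| Scale | Weeks 52 and 78, on drug | ET visit | Off-drug visits |
|---|---|---|---|
| ADAS-Cog, A-IADL, MMSE, NPI | yes | yes | yes |
| CDR, DAD, QoL-AD, RUD Lite | yes | yes | no |

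The schedules of assessments in both documents have no column for off-drug visits. RUD Lite is only summarised descriptively (SAP 8.2.4), so the gap matters for CDR-SB first, then DAD and QoL-AD.

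**2. The plan's own figure.** The documents give no effect, SD or power for CDR-SB. The nearest figure is completers: 300 × (1 − 0.17) = 249, against about 250 stated in SAP 4.1. With the 325 actually randomized, 17% is 55 subjects.

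**3. Who lacks a Week 78 CDR.** SAP Table 6 maps an ET value on Day 457–592 to Week 78. Assume stop days uniform on Day 2–546. The share of ET visits mapped to Week 78 is (546 − 457 + 1)/(546 − 2 + 1) = 90/545 = 0.165, so 0.835 of discontinuers have no Week 78 CDR. At 17% that is 0.17 × 0.835 = 0.142 of subjects, or about 46 of 325.

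**4. Size of the gap (illustration).** Let d be the share stopping drug (equal by arm, unrelated to outcome) and L the share of benefit lost by Week 78 among those with no Week 78 CDR. If the full on-drug effect is Δ, the MAR analysis returns about Δ, while the treatment-policy effect is Δ × (1 − 0.835 × d × L). Overstatement = 1/(1 − 0.835 × d × L) − 1.

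| d | L = 0.5 | L = 1 | L = 0 |
|---|---|---|---|
| 0.10 | 1/0.9583 − 1 = 4.4% | 1/0.9165 − 1 = 9.1% | 0 |
| 0.17 | 1/0.9290 − 1 = 7.6% | 1/0.8581 − 1 = 16.5% | 0 |
| 0.25 | 1/0.8956 − 1 = 11.7% | 1/0.7913 − 1 = 26.4% | 0 |

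A large-sample simulation agrees. It assumed Δ = −0.50 growing linearly by visit, change SDs of 1.2, 1.7 and 2.2 at Weeks 26, 52 and 78, correlations of 0.60–0.75, and ET values placed by Table 6 and treated as on-drug values at that visit. Half lost gave 4.2%, 7.3% and 11.8% at the three rates; all lost gave 9.0%, 16.3% and 25.7%; none lost gave 0.0–0.1%. When CDR was added at the off-drug visits with full attendance, the same model recovered the treatment-policy effect.

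**5. Opposite direction.** Suppose placebo discontinuers decline beyond the MAR prediction by one full drug effect. At d = 0.17 and L = 0.5 the treatment-policy effect is Δ × (1 − 0.0710 + 0.1420) = 1.0710Δ. The MAR estimate is then 1/1.0710 = 0.934 of it, an understatement of about 7%.

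**The case against.** - **The schedule may be softer than it looks.** SAP 8.3.1 and Protocol 10.7.2 promise every effort to continue visits and assessments, and Protocol 7.2.15 ends with a general invitation back at Week 78. A site could therefore perform a CDR, and it would be analysed. But none of these texts schedules one, and the itemised list and the synopsis point the other way.
- **MNAR is partly handled.** SAP 8.3.2 says it will be considered and names two methods, and 8.3.3 carries similar sensitivity analyses to the key secondaries. True; what is missing is commitment, a defined variant and timing before unblinding.
- **The problem is not unique to H3.** Discontinuers who are never retrieved meet the same MAR step on ADAS-Cog 13 and A-IADL, and off-drug attendance is only encouraged. The H3-specific increment is therefore unknown. The contrast with H2 also depends on which text in SAP 8.3.1 governs. The section describes a "likelihood based MMRM on treatment observed cases (OCs", yet also requires post-event data. Under the on-treatment reading, off-drug A-IADL values drop out too and the contrast disappears.
- **Treatment policy is not lost altogether.** For symptomatic medication started while on study drug, CDR visits continue. Subjects who must be withdrawn because memantine is judged necessary (Protocol 5.5) fall into the gap.
- **The estimand is written out only for ADAS-Cog 13.** This stands, but the sentence in 8.3.3 is explicit for the secondary endpoints.

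**Conclusion.** The point holds for CDR-SB and for study-drug discontinuation: the declared strategy is not supported by the scheduled data or the committed analyses. DAD and QoL-AD share the gap outside the alpha-controlled tests. The illustrative overstatement at 17% discontinuation is about 7% (half the benefit lost) to 16% (all lost), or 4–12% and 9–26% over 10–25% discontinuation. These figures rest on assumed timing, equal rates by arm and stopping unrelated to outcome. The 17% is the SAP's drop-out figure used as a stand-in for the study-drug discontinuation rate.

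Three stronger readings are not supported.

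- A reader might infer that alpha control fails. In the model above every gap is a multiple of the drug effect and vanishes when there is none, so no inflation is shown.
- A reader might infer gaps of 20% or 33%, from 1/0.83 and 1/0.75. Those figures apply full loss even to subjects whose ET value Table 6 already counts as Week 78.
- A reader might infer that the SAP must switch CDR-SB to a hypothetical strategy. Keeping treatment policy with a prespecified non-MAR analysis is equally coherent.

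**What to change.** Change the SAP text before unblinding:

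1. In 8.3.3, state that no CDR is scheduled after the ET visit, so the CDR-SB MMRM does not by itself estimate a treatment-policy effect for study-drug discontinuation. Word the H3 conclusion accordingly. The H3 test and its alpha stay with this MMRM.
2. For CDR-SB, turn the optional placebo-based pattern-mixture analysis in 8.3.2 into a commitment. Fix its variant now (for example jump-to-reference or copy-reference), because variants differ in how much benefit they retain. Add the tipping-point method as a further check and report both beside the MMRM.
3. State that all ET CDRs and any off-drug CDR that was collected stay in the analysis, as 8.3.1 requires.
4. In 8.3.1, reconcile the on-treatment observed-case wording with the instruction to include post-event data.

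The cost is SAP text and one analysis the plan already names; no new visits are needed. The downside is that the CDR-SB estimate offered for treatment policy may be smaller than the MMRM estimate.

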8.3.4 Subgroup Analyses

[figure not shown]
Efficacy analyses in the sub-groups of subjects with screening MMSE 22 to 26 (inclusive) and 27-30 (inclusive) will be performed on the FAS using the MMRM method. Efficacy analyses will also be performed in the subgroups defined by the use of AChEI (yes or no), age group (50-65 or > 65 years of age) and gender (female or male). These subgroup analyses will be performed on the FAS using the MMRM method for primary and key secondary endpoints.

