All subjects will be randomized to receive double-blind treatment consisting of either ALZ-801 265mg BID or matched placebo with similar appearance. Subjects will be randomized in a 1:1 ratio to either active or placebo arms. Subjects and their study partners, study personnel at the clinical sites and all Sponsor staff will remain blinded to treatment assignement till after database lock and unblinding. Double-blind treatment will be dispensed in blister packs. Details regarding the randomization stratification can be found in Section 3.1.

During the conduct of the study, the personnel who perform the unblinded safety analysis for the Data and Safety Monitoring Board (DSMB) will be shielded from the study team by a firewall and other appropriate standard operating procedures. These steps are further described and documented in the DSMB charter.

Subjects whose treatment assignment is unblinded for safety purposes will be listed and the reasons for unblinding will be documented prior to database lock and unblinding.

In the event that prescreening/baseline data were mistakenly entered into the Interactive Response Technology for randomization and stratification purposes, a listing of all such misstratifications will be provided. Using the intent-to-treat (ITT) principle, efficacy analyses for such subjects will be performed "as randomized". For the statistical models used for analyses, the "as randomized" variables corresponding to the stratification factors will be used as

For safety analyses, the correct stratification factors will be used to classify subjects in the actual stratification categories or subgroups.

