4.1 Primary Clinical Outcome

The target study sample size was 300 subjects randomized or 150 subjects per treatment group, based on ADAS-Cog 13, the primary clinical outcome. The study completed enrollment with 325 randomized subjects. The ADAS-Cog 13 is a well-validated and widely-used measure of global cognition in AD observational studies and Phase 3 drug trials. This scale evaluates multiple cognitive domains including memory, language, praxis, orientation, and executive function. To improve the sensivity of ADAS-Cog in MCI patients, two additional items were added to the original 11-item scale, including delayed word recall and digit cancellation (Mohs 1997).

Study Sample Size

Sample size determination was based on ADAS-cog results from an AD trial with tramiprosate, the active agent in ALZ-801. These efficacy data were observed in Mild AD patients (baseline MMSE =22-26) with APOE4/4 genotype who received tramiprosate 150mg BID over 78 weeks (Abushakra 2017). The tramiprosate 150mg BID dose provides plasma exposures similar to ALZ-801 at 265mg BID, the dose used in the current study.

In the 78-week tramiprosate Phase 3 study, the APOE4/4 Mild AD patients showed approximately 5.0-point difference from placebo (benefit) on ADAS-Cog. Since this Phase 3

For the primary efficacy outcome of ADAS-Cog 13, this study is powered to detect a 3.0-point difference between the active ALZ-801 treatment and the placebo in the CBL to Week 78. An increase in ADAS-Cog scores denotes cognitive worsening. It is expected that the mean baseline ADAS-Cog 13 in both groups will be 22.0 (standard deviation [SD] 6.7), which is expected to increase by 6 points in placebo (CBL: 6.0, SD 5.6), and 3 points in the active drug arm (CBL: 3.0, SD 8.1). A sample size of 125 completed subjects per arm will provide > 90% power to detect a difference of 3 points on ADAS-Cog. The drop-out rate is estimated to be approximately 17% at 78 weeks, thus a total of 300 subjects enrolled would provide approximately 250 completers (125 per arm).

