Recent trials of anti-amyloid antibodies in Early AD have shown ADAS-Cog effects of \leq 2.0 points at 78 weeks (Tolar 2020). A Phase 3 trial with aducanumab showed ADAS-cog effects versus placebo of \sim 1.8 points in APOE4 carriers (Budd-Haeberlein 2022). A Phase 2 trial with donanemab in Early AD showed ADAS-Cog effects of \sim 2.0 points (Mintun 2021). A Phase 3 trial of the approved amyloid antibody lecanemab in Early AD showed ADAS-Cog benefit of 1.44 points versus placebo (Van Dyck 2023). Therefore, we also considered a more conservative scenario where drug-placebo difference on ADAS-Cog is 2.5 points. The sample size of 125 completed subjects per arm (assuming 17% dropout rate) provides approximately 80% power to detect a difference of 2.5 points between the active treatment and the placebo at a significance level of α = 0.05 (2-sided).

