8.1.2 Hypothesis Testing

[figure not shown]
The Null Hypothesis of the study is that the CBL of ADAS-Cog 13 in ALZ-801 arm is not different from the placebo arm at 78 weeks.

The Alternate Hypothesis is that the CBL of ADAS-Cog 13 (Mohs 1997) in ALZ-801 arm is different from the placebo at 78 weeks.

The statistical testing will be two-sided and will be performed at the α =0.05 significance level. The key secondary efficacy endpoints will be compared only after the comparison of the primary endpoint has reached statistical significance. The comparisons of key secondary

endpoints will be done using a graphical approach (Bretz 2009) that strongly controls the family-wise Type 1 errors arising from multiple comparisons (Figure 2).

Figure 2 Graphical Approach Procedure for Analysis of Key Secondary Outcomes

[figure not shown]

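### The SAP analyses the treatment effect within subgroups but specifies no treatment-by-subgroup contrast, so a uniform effect can easily look specific to one MMSE stage

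*SAP*

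**What the plan says.** SAP 8.3.4 opens with disease stage: "Efficacy analyses in the sub-groups of subjects with screening MMSE 22 to 26 (inclusive) and 27-30 (inclusive) will be performed", on the FAS by MMRM. It then adds AChEI use, age group and gender, and closes: "These subgroup analyses will be performed on the FAS using the MMRM method for primary and key secondary endpoints". It gives no heterogeneity test, no between-subgroup estimate and no rule for reading results that differ between levels.

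The model it refers to is set out in SAP 8.3.1, Table 16 and the example code in SAP 8.3.2. Its only interaction is treatment by visit. AChEI use, age group, gender and MMSE group enter as main effects only.

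Protocol 10.7.4 foresees MMRM analyses by MMSE group and a subgroup analysis by AChEI use, also without an interaction test. SAP 8.1.5 treats p-values for the additional clinical endpoints as nominal but does not mention subgroups.

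**The concern.** A subgroup analysis asks whether the effect differs between levels, and the quantity that answers this is the difference between the two effects with its confidence interval. The plan produces two effects and leaves the comparison to the reader.

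This matters most for MMSE. The earlier tramiprosate signal came from Mild AD with MMSE 22-26 (Protocol 2.3.1.1, SAP 4.1). The extension to MMSE above 26 rests on an expectation (Protocol 2.3). Readers will therefore look at the two MMSE strata closely. If one has p<0.05 and the other does not, the natural reading is that the drug works at one stage only, and no planned display shows whether the data support that.

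**Working it through.** **Inputs**
- Test level (SAP 8.1.2): "The statistical testing will be two-sided and will be performed at the α =0.05 significance level". No separate level is given for subgroups, so two-sided 0.05 is assumed there too.
- Change from baseline and SDs (SAP 4.1): "increase by 6 points in placebo (CBL: 6.0, SD 5.6), and 3 points in the active drug arm (CBL: 3.0, SD 8.1".
- Effects considered (SAP 4.1): 3.0 points, and "we also considered a more conservative scenario where drug-placebo difference on ADAS-Cog is 2.5 points".
- Allocation (SAP, Randomization Schedule and Blinding Procedures): "Subjects will be randomized in a 1:1 ratio to either active or placebo arms".
- Dropout (SAP 4.1): "The drop-out rate is estimated to be approximately 17% at 78 weeks". Then 300 × 0.83 = 249, or about 125 completers per arm.
- MMSE shares (SAP 3.1): about 60% at 22-26 and 40% at 27-30, so 125 × 0.6 = 75 and 125 × 0.4 = 50 per arm at Week 78.
- AChEI share (Protocol 10.7.4): about 80% users, so 125 × 0.2 = 25 per arm without AChEI.

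**Step 1. Reproduce the plan's power.** Root-mean-square SD = √((8.1² + 5.6²)/2) = 6.963. With n per arm, SE = 6.963 × √(2/n) and power = Φ(δ/SE − 1.96). For n = 125, SE = 0.881.
- δ = 3.0: Φ(3.406 − 1.96) = 92.6%. The SAP says: "A sample size of 125 completed subjects per arm will provide > 90% power to detect a difference of 3 points on ADAS-Cog". This agrees.
- δ = 2.5: Φ(2.838 − 1.96) = 81.0%, against the SAP's approximate 80%. This agrees.

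**Step 2. Power within each MMSE stratum, with the same true effect in both.** SE is 1.137 for n = 75 and 1.393 for n = 50. The strata contain different subjects, so their results are independent. P(exactly one significant) = p₁(1 − p₂) + p₂(1 − p₁).

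| Uniform effect | Power, MMSE 22-26 | Power, MMSE 27-30 | Both | Exactly one | of which 22-26 only | Neither |
|---|---|---|---|---|---|---|
| 3.0 points | 75.1% | 57.7% | 43.3% | 46.1% | 31.8% | 10.5% |
| 2.5 points | 59.4% | 43.5% | 25.8% | 51.2% | 33.6% | 22.9% |

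Among trials with a significant overall result, exactly one stratum is significant in 47.9% (3.0 points) or 58.3% (2.5 points), from 2,000,000 simulated draws.

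**Step 3. Sensitivity.** With the 325 subjects actually randomized, 325 × 0.83 / 2 = 134.9 per arm, and the exactly-one figures are 43.8% and 51.0%. With 125 per arm at 3.0 points and MMSE shares from 50/50 to 70/30, the figure runs from 44.0% to 52.4%.

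**Step 4. AChEI.** At 80/20 and 3.0 points, power is 86.1% in users and 33.1% in non-users. Exactly one is significant in 0.861 × 0.669 + 0.331 × 0.139 = 62%.

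**Step 5. What the contrast would add.** For MMSE, SE of the difference = √(1.137² + 1.393²) = 1.80 points, so the 95% CI half-width is 1.96 × 1.80 = 3.5 points. When the effect is uniform, the interaction test is falsely significant in 5% of trials. Among trials with one stratum only significant, it is significant in 9 to 10%. Its power for a true 3-point difference between strata is Φ(3.0/1.80 − 1.96), about 39%. For 80% power the difference must be 1.80 × (1.96 + 0.84), about 5.0 points.

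**The case against.** Several stronger readings are tempting, and the documents do not support them.

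- A reader might infer that the plan compares subgroups by their separate p-values. It does not say so, and it nowhere announces a stage-specific claim. The 46-51% is the chance of a pattern that invites misreading. It is not the chance of a false conclusion drawn by the plan.
- A reader might infer that the trial could not tell a real difference between strata from chance. It could. SAP 8.3.1 provides the treatment difference with its standard error and CI. The strata are disjoint, so anyone can subtract the estimates and combine the standard errors as in Step 5. What is missing is a pre-specified estimate and display.
- A reader might take the upper MMSE stratum, at about 50 per arm, as the smallest subgroup. The no-AChEI subgroup is about half that at Week 78. These are also Week 78 counts. The MMRM uses every FAS subject with post-baseline data, so more subjects inform the covariance.
- Separate fits are not a fault in themselves. They let variance and covariate effects differ by stage, while one model imposes a common covariance unless told otherwise. The SAP does not actually state that separate models will be used, although that is the likelier reading.

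It is also fair to say that the consequence is limited. Subgroups lie outside the alpha-controlled family of three hypotheses in SAP 8.1.5, and the contrast has low power. Both points stand. They bear on how much the omission matters and do not remove it. The low precision is itself something the report should show, and separate p-values hide it.

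**Conclusion.** The point holds as a missing safeguard. SAP 8.3.4 specifies no treatment-by-subgroup contrast for any of its four factors, and nothing in the protocol or elsewhere in the SAP supplies one. On the plan's own inputs, a uniform effect of 2.5 to 3.0 points leaves exactly one MMSE stratum significant in about half of trials (46-51%), most often the 22-26 stratum.

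The figures assume equal SDs and dropout across strata, the stated shares among completers, and a two-group comparison of means at Week 78 in place of the MMRM. Baseline adjustment would change the powers somewhat. The pattern would remain common as long as power within a stratum is moderate.

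The test of the primary endpoint and the alpha control of the key secondary endpoints are not touched.

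**What to change.** Amend SAP 8.3.4 before unblinding:

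1. For each factor, fit one MMRM on the full FAS that adds subgroup-by-visit, treatment-by-subgroup and treatment-by-subgroup-by-visit terms, with the subgroup main effect. Report the Week 78 treatment-by-subgroup contrast with 95% CI and p-value, and take the within-subgroup differences from the same model. If the covariance is to differ by subgroup, obtain the contrast from the difference of the independent subgroup estimates instead. State in advance which route is used.
2. Use one MMSE definition for both the subgroup and the model term. SAP 8.3.4 uses screening MMSE. SAP 8.3.1 uses baseline MMSE (≤26 vs >26), which SAP 8.1.3 defines as the average of the screening and Visit 2 scores. The stratification factor is described as screening MMSE in SAP 3.1 and as Baseline Visit MMSE in Protocol 10.4. Without reconciliation, the interaction model would carry two overlapping MMSE factors.
3. Label within-subgroup p-values nominal, to be read only alongside the contrast. State that a non-significant contrast does not show homogeneity.

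The cost is SAP wording and four factors × three endpoints = 12 further model fits. No new data are needed. The price in interpretation is an imprecise contrast, with an MMSE interval of about ±3.5 points.
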